2.3 Informed Consent

Investigators must ensure that subjects are clearly and fully informed about the purpose, potential risks, and other critical issues regarding clinical studies in which they volunteer to participate.

In situations where consent cannot be given to subjects, their legally acceptable representatives (as per country guidelines) are clearly and fully informed about the purpose, potential risks, and other critical issues regarding clinical studies in which the subject volunteers to participate.

BMS will provide the investigator with an appropriate (ie, Global or Local) sample informed consent form which will include all elements required by ICH, GCP and applicable regulatory requirements. The sample informed consent form will adhere to the ethical principles that have their origin in the Declaration of Helsinki.

Investigators must:

- 1) Provide a copy of the consent form and written information about the study in the language in which the subject is most proficient prior to clinical study participation. The language must be non-technical and easily understood.
- 2) Allow time necessary for subject or subject's legally acceptable representative to inquire about the details of the study.
- 3) Obtain an informed consent signed and personally dated by the subject or the subject's legally acceptable representative and by the person who conducted the informed consent discussion.
- 4) Obtain the IRB/IEC's written approval/favorable opinion of the written informed consent form and any other information to be provided to the subjects, prior to the beginning of the study, and after any revisions are completed for new information.
- 5) If informed consent is initially given by a subject's legally acceptable representative or legal guardian, and the subject subsequently becomes capable of making and communicating his or her informed consent during the study, consent must additionally be obtained from the subject.
- 6) Revise the informed consent whenever important new information becomes available that is relevant to the subject's consent. The investigator, or a person designated by the investigator, should fully inform the subject or the subject's legally acceptable representative or legal guardian, of all pertinent aspects of the study and of any new information relevant to the subject's willingness to continue participation in the study. This communication should be documented.

The confidentiality of records that could identify subjects must be protected, respecting the privacy and confidentiality rules applicable to regulatory requirements, the subjects' signed ICF and, in the US, the subjects' signed HIPAA Authorization.

The consent form must also include a statement that BMS and regulatory authorities have direct access to subject records.

Subjects unable to give their written consent (eg, stroke or subjects with or severe dementia) may only be enrolled in the study with the consent of a legally acceptable representative. The subject must also be informed about the nature of the study to the extent compatible with his or her understanding, and should this subject become capable, he or she should personally sign and date the consent form as soon as possible. The explicit wish of a subject who is unable to give his or her written consent, but who is capable of forming an opinion and assessing information to refuse participation in, or to be withdrawn from, the clinical study at any time should be considered by the investigator.

The rights, safety, and well-being of the study subjects are the most important considerations and should prevail over interests of science and society.

3 INVESTIGATIONAL PLAN

3.1 Study Design and Duration

This is a randomized, active-controlled, staged, open-label clinical trial. Approximately 200 treatment-experienced HIV-1 subjects will be randomized to one of five treatment arms (approximately 40 per arm) in a staged fashion.

The data from the Week 24 analysis of Stage 1 and AI468038, including safety, efficacy and pharmacokinetics, will be examined to trigger the start of Stage 2 and confirm the two doses of BMS-955176 for study in Stage 2.

Stage 1:

In Stage 1, subjects will be randomly assigned 1:1 to one of two treatment arms and on Day 1 will begin dosing with:

- Arm 1 : BMS-955176 120 mg QD + ATV/r 300/100 mg QD + DTG 50 mg QD, or
- Arm 2: TDF 300 mg QD + ATV/r 300/100 mg QD + DTG 50 mg QD

Stage 2:

In Stage 2, subjects will be randomly assigned 1:1:1 to one of three treatment arms and on Day 1 will begin dosing with:

- Arm 3: BMS-955176 120 mg QD + ATV 400 mg QD + DTG 50 mg QD, or
- Arm 4: BMS-955176 180 mg QD + ATV 400 mg QD + DTG 50 mg QD, or
- Arm 5: TDF 300 mg QD + ATV/r 300/100 mg QD + DTG 50 mg QD

3.1.1 Screening

The screening period begins with the subject's signature on the informed consent form (ICF).

The subject is then enrolled via the Interactive Voice Response System IVRS (or its web-based equivalent) See [Section 4.4](#).

If the subject meets all eligibility criteria, the subject must be randomized within the 42 day screening period.*

* If, within the 42-day screening window, the resistance results have not yet been reported, the screening window may be extended up to 60 days for only these results.

3.1.2 Day 1/Baseline Visit

3.1.2.1 Day 1/Baseline Visit for Arms 1 and 2 - Stage 1

In Stage 1, approximately 80 subjects will be randomized 1:1 (approximately 40 per arm) to either of the treatment arms containing boosted atazanavir (ATV/r).

On the Day 1 Visit, subjects in Arms 1 and 2 will begin QD dosing with BMS-955176 or TDF, each in combination with ATV/r and DTG (see [Section 4.5](#) for additional details of Selection and Timing of Dose).

- Arm 1 : BMS-955176 120 mg QD + ATV/r 300/100 mg QD + DTG 50 mg QD, or
- Arm 2: TDF 300 mg QD + ATV/r 300/100 mg QD + DTG 50 mg QD

3.1.2.2 Day 1/Baseline Visit for Arms 3, 4 and 5 - Stage 2

In Stage 2, approximately 120 subjects will be randomized 1:1:1 (approximately 40 per arm) to either of the two BMS-955176 treatment arms containing ATV, or to the TDF Arm.

On the Day 1 Visit, subjects will begin QD dosing with BMS-955176 in combination with ATV and DTG, or TDF in combination with ATV/r and DTG (see [Section 4.5](#) for additional details of Selection and Timing of Dose).

- Arm 3: BMS-955176 120 mg QD + ATV 400 mg QD + DTG 50 mg QD, or
- Arm 4: BMS-955176 180 mg QD + ATV 400 mg QD + DTG 50 mg QD, or
- Arm 5: TDF 300 mg QD + ATV/r QD 300/100 mg + DTG 50 mg QD

3.1.3 Week 2 Intensive PK Visit

Subjects with anemia, defined as Hemoglobin < 11.0 g/dL, should be excluded from participation in the Week 2 Intensive PK Substudy.

Subjects in all arms will have the opportunity to participate in an elective Intensive PK Substudy visit at Week 2 (window for visit: Day 12-16). Approximately 60 subjects, 12 subjects from each arm, are expected to participate in the substudy; BMS may allow the substudy to over-enroll in an effort to have a sufficient number of complete datasets.

The series of 12 blood draws begins with pre-dose (0-hour) blood samples to be collected approximately 24 hours (20-28 hrs) after the morning doses of study drugs that were taken on the day before. Ten more samplings are drawn through the 12-hr time point, with one final sampling collected at the 24-hr time point, requiring the subject to either remain overnight in the clinic, or to return the next morning; the final 24-hr sample will be collected prior to administration of the morning doses of study drugs (See [Section 5.5.1](#)).

PK Tools/Job Aids will be provided to assist with the proper sequencing of dosing and blood sample collections, as well as the collection of required data.

3.1.4 Visits Week 4 - 96

Subjects are expected to be treated for the duration of 96 weeks. In each Stage, after Day 1 and the optional Intensive PK visit at Week 2, subjects will be required to attend 12 more in-clinic study visits over the 96-week treatment period, as follows:

- Visits are conducted every 4 weeks from Week 4 through Week 16
- Visits are conducted every 8 weeks from Week 24 through Week 48
- Visits are conducted every 12 weeks from Week 60 through Week 96

Visits should be scheduled as an interval from the Day 1/Randomization date, and within a window of 5 days earlier or later.

One of the visits Week 4 - 24 should meet the very specific timing requirements as outlined in [Section 5.5.2](#) for a pre-AM dose blood collection.

Telephonic visits will be conducted with each subject at visit Weeks 20, 28, 36, 44, 54, 66, 78, and 90 to conduct an adherence assessment and to continue retention efforts

3.1.5 Selection of the Continuation Dose of BMS-955176

3.1.5.1 Selection of the Continuation Dose, and the Switch for Stage 1

Once all subjects in Stage 1 have reached Week 24*, BMS will conduct an interim analysis of efficacy, safety, resistance and pharmacokinetics.

As described in [Section 8.4.7](#), an analysis of Virologic Futility will also occur. If Arm 1 meets criteria for Virologic Futility at Week 24, the clinical trial will be terminated.

The Week 24 analysis of Arms 1 and 2, combined with the Week 24 analysis of all Arms in the AI468038 study, will be used to select a Continuation Dose of BMS-955176 for Arm 1 in this study. Subjects in the BMS-955176 Treatment Arm 1 may subsequently be transitioned to a selected Continuation Dose.

Subjects in the Arm containing TDF will continue with the TDF treatment regimen.

The assigned backbone will not change.

The Week 24 efficacy, safety, and pharmacokinetic analyses from Stage 1 and study AI468038 will also trigger the start of Stage 2.

** If the Continuation Dose cannot be clearly identified using the Week 24 data, the study will continue in original fashion until an analysis of the Week 48 data can be performed and the Continuation Dose is selected. If a Continuation Dose cannot be selected based upon the Week 24 data, this does not preclude the ability to start recruitment of Stage 2.*

After the Continuation Dose is selected, and once all of the logistics (eg, distribution of clinical drug supplies, activation of the new portion of the IVRS) have been completed globally, the transition of the subjects in Arm 1 to the Continuation Dose will occur. It is anticipated that this transition will occur on or after all subjects have reached Week 48 (the earliest subjects to begin study treatment could be well beyond Week 48 when the switch to the Continuation Dose occurs).

3.1.5.2 Selection of the Continuation Dose, and the Switch for Stage 2

Once all subjects in Stage 2 have reached Week 24, BMS will conduct an analysis of efficacy, safety, resistance and pharmacokinetics.

As described in [Section 8.4.7](#), an analysis of Virologic Futility will also occur. If a BMS-955176 dose arm meets criteria for Virologic Futility at Week 24, subjects in said arm will begin dosing with the next highest available remaining dose of BMS-955176.

The data from AI468038 and AI468048 (Stages 1 and 2) will be used to select a Continuation Dose of BMS-955176 for Arms 3 and 4. Subjects in the BMS-955176 Treatment Arms 3 and 4 will subsequently be transitioned to a selected Continuation Dose. It is anticipated that this transition may occur on or after all subjects have reached Week 48, or it could occur sooner after Week 24.

The assigned backbone will not change.

[figure not shown]
Subjects in the arm containing TDF will continue with this assigned treatment regimen.

3.1.6 End of the study

The end of the study will occur when the last study visit has been completed, defined as the final subject completing their final study visit (expected to be a Week 96 or Early Termination visit).

The study design schematic is presented in [Figure 3.1.6-1](#).

Figure 3.1.6-1: Study Design Schematic

3.2 Post Study Access to Therapy

At the conclusion of the study, subjects who continue to demonstrate clinical benefit will be eligible to receive BMS supplied study drug. Study drug will be provided via an extension of the study, a rollover study requiring approval by responsible health authority and ethics committee or through another mechanism at the discretion of BMS. BMS reserves the right to terminate access to BMS supplied study drug if any of the following occur: a) the marketing application is rejected by responsible health authority; b) the study is terminated due to safety concerns; c) the subject can obtain medication from a government sponsored or private health program; or d) therapeutic alternatives become available in the local market.

3.3 Study Population

For entry into the study, the following criteria MUST be met.

3.3.1 *Inclusion Criteria*

1. Signed Written Informed Consent

- a) Ability to understand and sign a written informed consent form

2. Target Population

- a) Antiretroviral treatment-experienced, defined as having documented evidence of having failed at least 1 ARV regimen (with or without documented resistance)
 - i) Failure could be due (but is not limited) to cART intolerance, sub-optimal adherence, or an adverse event
- b) Screening Plasma HIV-1 RNA \geq 400 copies/mL (An initial, pre-screening value from Investigator must demonstrate HIV-1 RNA > 40 c/mL)
- c) CD4+ T-cell count > 50 cells/mm³
- d) Screening genotype/phenotype indicating susceptibility to study drugs (unboosted ATV, FC < 2.2 ; DTG; TDF)
- e) Estimated Life expectancy \geq 1 year

Subject Re-enrollment: This study permits the re-enrollment of a subject that has discontinued the study as a pre-treatment failure (ie, subject has not been randomized / has not been treated). If re-enrolled, the subject must be re-consented and assigned a new PID. (See [Section 5.5.1](#) for additional details.)

3. Age and Reproductive Status

- a) Males and non-pregnant females
- b) At least 18 years of age, (or minimum age as determined by local regulatory or as legal requirements dictate)
- c) Willingness to use approved highly effective methods of contraception (see below) to avoid pregnancy (female subjects who are WOCBP or female partners of male subjects who are sexually active with WOCBP)

- d) Women of childbearing potential (WOCBP) must have a negative serum or urine pregnancy test (minimum sensitivity 25 IU/L or equivalent units of HCG) within 24 hours prior to the start of study drug.
- e) Women must not be breastfeeding
- f) WOCBP must agree to follow instructions for method(s) of contraception for the duration of treatment with study drug BMS-955176 plus 5 half-lives of the study drug BMS-955176 (8 days) plus 30 days (38 days) post-treatment completion.
- g) Males who are sexually active with WOCBP must agree to use a condom for the duration of treatment with study drug BMS-955176 plus 5 half-lives of the study drug BMS-955176 (8 days) post-treatment completion.

Investigators shall counsel WOCBP and male subjects who are sexually active with WOCBP on the importance of pregnancy prevention and the implications of an unexpected pregnancy. Investigators shall advise WOCBP and male subjects who are sexually active with WOCBP on the use of highly effective methods of contraception.

All subjects must agree to the use of a highly effective method of contraception as listed below.

HIGHLY EFFECTIVE METHODS OF CONTRACEPTION FOR FEMALE SUBJECTS WHO ARE WOCBP, MALE SUBJECTS AND THEIR FEMALE PARTNERS (WHO ARE WOCBP)

Highly effective methods of contraception have a failure rate of < 1% when used consistently and correctly. WOCBP and female partners of male subjects, who are WOCBP, are expected to use one of the highly effective methods of contraception listed below.

Study subjects who are WOCBP cannot use hormonal methods of contraception as one of the highly effective methods of contraception because there are data to show a lack of effectiveness of systemic hormonal contraceptives in women taking BMS-955176. However, WOCBP can continue to use hormonal contraceptives, if necessary, in addition to one other non-hormonal highly effective methods of contraception.

Male subjects must inform their female partners who are WOCBP of the contraceptive requirements of the protocol and are expected to adhere to using contraception with their partner. Relevant exposure of BMS-955176 in female partners of male participants in the study is expected to be negligible. Female partners of male subjects participating in the study may use hormone based contraceptives as one of the acceptable methods of contraception because exposure to the investigational product would be too small to alter exposure of hormonal contraceptives.

1. IUDs
2. Bilateral tubal occlusion
3. Vasectomised partner with documented azoospermia 90 days after procedure
 - o Vasectomised partner is a highly effective birth control method provided that partner is the sole sexual partner of the WOCBP trial participant and that the vasectomised partner has received medical assessment of the surgical success.

4. Complete abstinence

- Complete abstinence is defined as the complete avoidance of heterosexual intercourse when this is the preferred lifestyle of the patient.
- Complete abstinence is an acceptable form of contraception for all study drugs and must be used throughout the duration of study and for the duration of time as specified above.
- It is not necessary to use any other method of contraception when complete abstinence is elected.
- Subjects who choose complete abstinence must continue to have pregnancy tests.
- Acceptable alternate methods of highly effective contraception must be discussed in the event that the subject chooses to forego complete abstinence

The reliability of sexual abstinence needs to be evaluated in relation to the duration of the clinical trial and the preferred and usual lifestyle of the subject.

3.3.2 *Exclusion Criteria*

1. Target Disease Exceptions

- a) Antiretroviral treatment-experienced adults who have failed < 1 ARV regimen
- b) Resistance or partial resistance to any study drug
- c) Three or more of the following PI mutations, historical or documented: M36I/V, M46I/L/T, G48M/V, I54V/L/T/M/A, G73S/A/C/T, V82A/F/T/S/I, or L90M
- d) Any major ATV mutations, historical or documented: I50L, I84V/A, N88D/S
- e) Any major TDF mutation, historical or documented: K65R or T69ins
- f) Three or more of the following non-accessory thymidine analogue mutations (TAMs): M41L, D67N, K70R, L210W, T215Y/F, K219Q/E
- g) Any major mutations for raltegravir (RAL), elvitegravir (or clinically suspected INI resistance), historical or documented: T66IAK, E92Q, S147G, N155H, Q148H/K/R, Y143C/H/R, E157Q
- h) Antiretroviral treatment-experienced adults infected with Clade AE
- i) Patients who have failed a previous boosted PI- or Integrase strand transfer inhibitor (INSTI)-containing regimen for which resistance analyses were not conducted at the time of failure
- j) Prior exposure to BMS-955176

2. Medical History and Concurrent Diseases

- a) A new AIDS defining condition diagnosed within the 30 days prior to screening (see [Appendix 2](#))
- b) Any other clinical condition (including but not limited to active substance use) or prior therapy that, in the opinion of the Investigator, would make the subject unsuitable for the study; unable to comply with dosing requirements; or unable to comply with study visits; or a condition that could affect the absorption, distribution, metabolism or excretion of the drug.

3. Physical and Laboratory Test Findings

- a) Chronic HBV/HCV (Positive blood screen for HBsAg; Positive blood screen for HCV Ab and HCV RNA)
- b) ALT or AST $> 3 \times$ ULN
- c) Alkaline Phosphatase $> 5 \times$ ULN
- d) Bilirubin $\geq 1.5 \times$ ULN
- e) History of decompensated cirrhosis or active decompensated cirrhosis
- f) Hemoglobin < 8.0 g/dL
- g) Platelets $< 50,000$ cells/mm³
- h) Estimated eGFR < 60 mL/min (CKD-EPI formula)
- i) Confirmed QT value > 500 msec at Screening or Day 1
- j) Confirmed QTcF value > 470 msec for women and > 450 msec for men at Screening or Day 1
- k) Confirmed PR Interval > 260 msec (severe first degree AV block) at Screening or Day 1
- l) Confirmed second or third degree heart block at Screening or Day 1

4. Allergies and Adverse Drug Reaction

- a) Medications contraindicated for use with investigational/non-investigational study drugs (ATV, RTV, DTG, TDF); or subjects with any known allergies to the investigational/non-investigational study drugs (ATV, RTV, DTG, TDF)
- b) Current or anticipated treatment with any of the medications listed in [Appendix 1](#), in addition to any medications that are contraindicated with ATV, RTV, DTG or TDF
- c) Participation in an experimental drug and/or HIV-1 vaccine trial(s) within 30 days prior to Screening

5. Other Exclusion Criteria

- a) Prisoners or subjects who are involuntarily incarcerated
- b) Subjects who are compulsorily detained for treatment of either a psychiatric or physical (eg, infectious disease) illness

Eligibility criteria for this study have been carefully considered to ensure the safety of the study subjects and that the results of the study can be used. It is imperative that subjects fully meet all eligibility criteria.

3.3.3 *Women of Childbearing Potential*

A woman of childbearing potential (WOCBP) is defined as any female who has experienced menarche and who has not undergone surgical sterilization (hysterectomy or bilateral oophorectomy) and is not postmenopausal. Menopause is defined as 12 months of amenorrhea in a woman over age 45 years in the absence of other biological or physiological causes. In addition, females under the age of 55 years must have a serum follicle stimulating hormone, (FSH) level > 40 mIU/mL to confirm menopause.

Females treated with hormone replacement therapy, (HRT) are likely to have artificially suppressed FSH levels and may require a washout period in order to obtain a physiologic FSH level. The duration of the washout period is a function of the type of HRT used. The duration of the washout period below are suggested guidelines and the investigators should use their judgement in checking serum FSH levels. If the serum FSH level is > 40 mIU/mL at any time during the washout period, the woman can be considered postmenopausal:

- 1 week minimum for vaginal hormonal products (rings, creams, gels)
- 4 week minimum for transdermal products
- 8 week minimum for oral products

Other parenteral products may require washout periods as long as 6 months.

3.4 Concomitant Treatments

3.4.1 Prohibited and/or Restricted Treatments

Refer to [Appendix 1](#) which details prohibited and precautionary therapies during the study, including specifics about the use of antacids and hormonal methods of contraception.

3.4.2 Other Restrictions and Precautions

None.

3.5 Discontinuation of Subjects following any Treatment with Study Drug

Subjects MUST discontinue investigational product (and non-investigational product at the discretion of the investigator) for any of the following reasons:

- Subject's request to stop study treatment
- Any clinical adverse event (AE), laboratory abnormality or intercurrent illness which, in the opinion of the investigator, indicates that continued participation in the study is not in the best interest of the subject
- Termination of the study by Bristol-Myers Squibb (BMS)
- Loss of ability to freely provide consent through imprisonment or involuntarily incarceration for treatment of either a psychiatric or physical (eg, infectious disease) illness
- Pregnancy (subjects should be discontinued in an appropriate manner)
- Repeat non-adherence by the subject with the requirements of the protocol or treatment (as determined by Investigator in consultation with the BMS Medical Monitor)
- Evidence of Hepatitis B or C infection
- Failure to achieve $> 1 \log_{10}$ c/mL decrease in HIV-1 RNA by Week 8
- Confirmed plasma HIV-1 RNA ≥ 1000 c/mL after Week 24
- Confirmed plasma HIV-1 RNA ≥ 200 c/mL after Week 48
- Emergence of genotypic and/or phenotypic resistance to any component of the study treatment regimen at any time after Screening
- Subject requires switching to any other ARV

- Development of pDILI (potential drug induced liver injury)
- Confirmed QTcB or QTcF value > 500 msec
- Confirmed second degree (Type II) or third degree AV block at any time during the study

In the case of pregnancy, the investigator must immediately notify the BMS Medical Monitor/designee of this event. The study drug will be permanently discontinued in an appropriate manner.

All subjects who discontinue study drug should comply with protocol specified follow-up procedures as outlined in [Section 5](#) (ie, perform an Early Termination [ET] visit). The only exception to this requirement is when a subject withdraws consent for all study procedures including post-treatment study follow-up (no such period exists in this study) or loses the ability to consent freely (ie, is imprisoned or involuntarily incarcerated for the treatment of either a psychiatric or physical illness).

If study drug is discontinued prior to the subject's completion of the study, the reason for the discontinuation must be documented in the subject's medical records and entered on the appropriate case report form (CRF) page.

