^b By definition, a pharmacodiagnostic sample (PDx) is a pre-treatment test to determine whether or not a patient is likely to respond to a drug (ie, a predictive test). Based on the results of clinical studies with BMS-955176, BMS may have to develop a PDx assay. Thus, PDx samples obtained at Screening in this study would be used for that sole purpose.

Table 5.1-2: Short-term Procedural Outline (AI468048)

Procedure	In-clinic Visit Day 1	In-Clinic Visit Optional Week 2 for Intensive PK (Day 12-16)	In-Clinic Visits Weeks 4, 8, 12, 16, 24, 32, 40, 48, 60, 72, 84, 96, and/or Early Termination (ET) (± 5 days)	Phone Visits Weeks 20, 28, 36, 44, 54, 66, 78, 90 (± 5 days)	Notes
Eligibility Assessments					
Inclusion/Exclusion Criteria	X				
Non-Laboratory Safety Assessments					
Full Physical Examination			WK 12, 24, 48, 96/ET		See Section 5.3.1 for requirements
Targeted Physical Examination	X		WK 4, 8, 16, 32, 40, 60, 72, 84		See Section 5.3.1 for requirements
Vital Signs & Physical Measurements	X		X		See Section 5.3.1 for requirements
Adherence Assessments			X	X	Including review of Dosing Diaries
Pre-treatment Events	X				See Table 5.1-1
Adverse Events Assessments	X	X	X		Serious and Non-serious AEs
Concomitant Medications	X	X	X		See Section 5.3.3
ECG	X		WK 4, 12, 24, 48, 96/ET		See Section 5.3.4 for requirements
Pregnancy Test	X	X	X		For females under age 55, an FSH level must be on record to confirm she is not a WOCBP if pregnancy testing is not being performed. If positive urine, request serum hCG quant. on lab requisition.

Table 5.1-2: Short-term Procedural Outline (AI468048)

Procedure	In-clinic Visit Day 1	In-Clinic Visit Optional Week 2 for Intensive PK (Day 12-16)	In-Clinic Visits Weeks 4, 8, 12, 16, 24, 32, 40, 48, 60, 72, 84, 96, and/or Early Termination (ET) (± 5 days)	Phone Visits Weeks 20, 28, 36, 44, 54, 66, 78, 90 (± 5 days)	Notes
Provide WOCBP with Home Pregnancy test kit(s) to be used during the in-clinic visit interval			WK 16, 24, 32, 40, 48, 60, 72, 84		Provide One Kit at Weeks 16 - 40 Provide Two Kits at Weeks 48 - 84 WOCBP subjects perform test Q4 weeks at home and report results to site.
Laboratory Assessments for Safety and Efficacy and Other Endpoints (See Appendix 5 for full details)					
Fasting Chemistry	X		X		Fasting overnight
Fasting Lipid Panel	X		WK 4, 12, 24, 48, 96/ET		Fasting overnight
Hematology	X		X		
Urinalysis	X		X		

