5.3 Safety Assessments

The investigative team should follow the protocol-specified schedule of safety-related measurements. Only data for the procedures and assessments specified should be submitted to BMS on the case report form. Additional procedures and assessments may be performed as part of standard of care, however, data for these assessments should remain in the subject's medical record and should not be submitted to BMS, unless specifically requested (ie, as part of an SAE).

5.3.1 *Vital Signs and Physical Examinations*

The schedule of vital signs, physical examinations, and targeted physical examinations is provided in [Section 5.1](#) (Flow Chart/Time and Events Schedule). Vital signs include heart rate, blood pressure, respiration rate, and temperature and should be measured after the subject has been sitting/resting for at least 5 minutes. Physical measurements include height and weight. Targeted physical examinations will include examination of the heart, lungs, skin, abdomen, any symptomatic organ system, and general appearance.

5.3.2 *Adverse Events*

Subjects will be closely monitored throughout the study for any new or ongoing HIV-related diagnoses ([Appendix 2](#)) and/or adverse events. CDC Class C events that occur from the Screening Visit through Day 1 (prior to dosing), will be recorded as Pre-treatment Events. All events that occur after dosing on Day 1 will be recorded on the appropriate Adverse Event eCRF. Additional information on Adverse Events is provided in [Section 6](#).

5.3.3 *Concomitant Medication Assessment*

All medications taken from the Screening Visit throughout the duration of the study will be reported. In addition, any prior therapy with antiretroviral drugs will be reported (See [Appendix 1](#) for Prohibited and Precautionary Therapies).

5.3.4 *Electrocardiograms*

The schedule of electrocardiograms (ECGs) is provided in Section 5.1 (Flow Chart/Time and Events Schedule). ECG machines will be provided by a central vendor who will also perform the read/interpretation of the output.

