PR	atrial depolarization to ventricular depolarization
PT	prothrombin time
PTT	partial thromboplastin time
QC	quality control
QD, qd	quaque die, once daily
QRS	interval representing the time for ventricular depolarization
QT	Duration of ventricular electrical activity
QTcF	QT corrected for heart rate using Frederica's formula
RAL	raltegravir
RBC	red blood cell
RNA	ribonucleic acid
RTV	ritonavir
SAD	single ascending dose
SDD	spray-dried dispersion
SAE	serious adverse event
SAP	statistical analysis plan
SD	standard deviation
SDTM	Study Data Tabulation Model
SOP	Standard Operating Procedures
SP1	spacer peptide 1
Subj	subject
STR	single tablet regimen
t	temperature
T	time
TDF	tenofovir

Term	Definition
TDF/FTC	Truvada (TDF 300 mg + FTC 200 mg)
TAO	Trial Access Online, the BMS implementation of an EDC capability
TAM	Thymidine analogue mutation
T-HALF	Half life
T-HALF _{eff} _AUC	Effective elimination half life that explains the degree of AUC accumulation observed
T _{max} , TMAX	time of maximum observed concentration
TR_AUC(0-T)	AUC(0-T) treatment ratio
TR_AUC(INF)	AUC(INF) treatment ratio
TR_Cmax	Cmax treatment ratio
UGT	UDP-glucuronosyltransferase
ULN	upper limit of normal
US	United States
VF	virologic failure
VK	Viral kinetics
VLP	Virus-like particles
WBC	white blood cell
WFD	Wallingford, Connecticut, USA
WHO	World Health Organization
Wk or WK	week
WOCBP	women of childbearing potential

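### No entry criterion limits QTcB, yet a confirmed QTcB above 500 msec is a mandatory stop, so a subject can be dosed while already over the stopping threshold

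*Protocol*

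**What the plan says.** Two of the physical and laboratory exclusions in Protocol Section 3.3.2 concern the QT interval. Item 3(i) excludes on "Confirmed QT value > 500 msec at Screening or Day 1", and item 3(j) on "Confirmed QTcF value > 470 msec for women and > 450 msec for men at Screening or Day 1". The other ECG exclusions are "Confirmed PR Interval > 260 msec (severe first degree AV block) at Screening or Day 1" and any confirmed second or third degree heart block. None mentions QTcB or heart rate.

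Section 3.5 introduces its list of stopping reasons with "Subjects MUST discontinue investigational product (and non-investigational product at the discretion of the investigator) for any of the following reasons". One item on that list is "Confirmed QTcB or QTcF value > 500 msec". It makes no reference to the baseline ECG or to change from baseline.

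ECGs are taken at Screening and Day 1 (Tables 5.1-1 and 5.1-2), and on treatment at "WK 4, 12, 24, 48, 96/ET". Section 5.3.4 adds that "ECG machines will be provided by a central vendor who will also perform the read/interpretation of the output".

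**The concern.** The other ECG stopping reasons in Section 3.5 are matched by an entry rule at least as strict. The QTcF stop at 500 msec lies 30 msec above the entry limit for women and 50 msec above that for men. The AV-block stop (Type II second degree, or third degree) is covered by excluding all second and third degree block at entry. QTcB is the one ECG stopping parameter with no counterpart at entry.

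The two corrections agree at 60 bpm and diverge as heart rate rises, QTcB becoming the larger. A subject with a high but permitted QTcF and a fast resting rate may therefore meet the stopping threshold before the first dose. If the same reading is confirmed on treatment she must stop, although the drug has changed nothing. Atazanavir is investigational product and is given in every arm (Section 4.1), so this applies to the tenofovir arms as well.

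For a viraemic, treatment-experienced patient that is an avoidable interruption of therapy. It could also reach the primary endpoint. Section 8.4.2.1 keeps all treated subjects in the denominator, and Section 8.3.1 needs an on-treatment HIV-1 RNA value in the Week 24 window.

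**Working it through.** **Inputs.** The entry limits are uncorrected QT 500 msec and QTcF 470 msec (women) or 450 msec (men), from Section 3.3.2. The stopping limit is QTcB or QTcF 500 msec, from Section 3.5. The abbreviation list (Section 11) defines QTcF as "QT corrected for heart rate using Frederica's formula", the cube-root correction. QTcB is not defined there; I take it to be the usual square-root (Bazett) correction. Heart rates below are assumed values, because the protocol gives no distribution.

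**Formulae.** With RR = 60/HR in seconds:

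- QTcF = QT / RR^(1/3)
- QTcB = QT / RR^(1/2)
- hence QTcB = QTcF × (HR/60)^(1/6)

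Setting QTcB = 500 gives HR = 60 × (500/QTcF)^6. The uncorrected QT at that rate is QTcF × (60/HR)^(1/3).

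| QTcF (msec) | Heart rate at which QTcB = 500 (bpm) | Uncorrected QT there (msec) |
|---|---|---|
| 470 (limit, women) | 87.0 | 415.3 |
| 465 | 92.7 | 402.2 |
| 460 | 98.9 | 389.3 |
| 450 (limit, men) | 112.9 | 364.5 |

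**Worked case.** A woman has QT 413.7 msec at 88 bpm, so RR = 60/88 = 0.682 s. Her QTcF is 413.7 / 0.682^(1/3) = 470 msec, which is eligible. Her QTcB is 413.7 / 0.682^(1/2) = 501 msec, above the stop.

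**Width of the gap.** The QTcF above which QTcB exceeds 500 msec is 500 × (60/HR)^(1/6):

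| Heart rate (bpm) | QTcF giving QTcB = 500 (msec) | Permitted QTcF range inside the gap |
|---|---|---|
| 80 | 476.6 | none (above both limits) |
| 90 | 467.3 | women: top 470 − 467.3 = 2.7 msec; men: none |
| 100 | 459.2 | women: top 470 − 459.2 = 10.8 msec; men: none |
| 110 | 452.0 | women: top 470 − 452.0 = 18.0 msec; men: none |
| 120 | 445.4 | women: top 470 − 445.4 = 24.6 msec; men: top 450 − 445.4 = 4.6 msec |

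**Does the uncorrected-QT exclusion help?** No. Within the QTcF limits, uncorrected QT can exceed 500 msec only below 60 × (470/500)^3 = 49.8 bpm in women or 60 × (450/500)^3 = 43.7 bpm in men. It guards the slow end of the heart-rate range, and this gap is at the fast end.

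**Effect on the endpoint.** Of the scheduled on-treatment ECGs, only those at Weeks 4 and 12 precede the Week 24 visit. One stop before that visit costs at most 1/40 = 2.5 points of an arm's response rate, if the subject would otherwise have responded. At the expected 80% response the average cost is 0.80 × 2.5 = 2.0 points. For scale, the protocol's own exact interval for 32 of 40 reproduces as 64.4% to 90.9% (stated as 64% to 91%), a width of 26.5 points.

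**The case against.** The strongest reply is that the two rules need not match. Entry selects on one correction, with sex-specific limits well below the stop. The on-treatment rule errs towards safety by acting on whichever correction is worse. Nothing in the protocol says QTcB was meant to govern eligibility. That is a defensible design, but it does not explain why someone already over a mandatory stopping threshold should be given a first dose.

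Several conditions must coincide, and the stop needs a confirmed value, so a single fast tracing does not trigger it. The limited size of the problem stands. Confirmation does not, however, filter out a subject whose usual resting rate is around 90 bpm. The only sex breakdown shown, from the Phase 2a study (Table 1.4.1.3-1), sums to 93 men among 97 subjects. That is a different population, but it lends no support to a large exposed group.

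Exclusion 2(b) lets an investigator turn away a subject judged unsuitable, and Section 5.9 has central ECG reads sent to sites as they become available. Both help, but exclusion 2(b) is discretionary, whereas the stop is numeric and compulsory.

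Finally, an entry limit of exactly 500 msec leaves no headroom: someone at 499 msec could cross through a slightly faster heart rate alone. That also stands. The remedy below prevents entry above the threshold; it does not prevent every stop unrelated to drug.

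**Conclusion.** The gap is real and follows directly from the two sections. No stated criterion keeps out a subject whose baseline QTcB already exceeds 500 msec. In women at the QTcF limit it opens at about 87 bpm, and in men only above about 113 bpm. At 80 bpm it does not exist.

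The point is minor. Few subjects are likely to be affected, and without a QTcF, heart-rate or sex distribution for this trial no number can be given. The most that one early stop can cost an arm is 2.5 points, small beside the planned interval, and the rule acts alike in all arms. The conclusion rests on QTcB being the square-root correction and on the same reading being confirmed on treatment.

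**What to change.** Leave the Section 3.5 stop as it is. Add one item to Section 3.3.2(3) excluding a confirmed QTcB above 500 msec at Screening or Day 1, taken from the central read. Nobody then starts treatment already over the stopping threshold, and no safety protection is weakened.

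The cost is one line of text and an occasional extra screen failure. The ECGs are already taken at both visits and read centrally, and QTcB follows from the QT and heart rate on the same tracing. As with the existing Day 1 ECG exclusions, the Day 1 reading has to be available before dosing for the criterion to work. If headroom is also wanted, the QTcB entry limit could be set below 500 msec, at the price of more screen failures.
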